Christensen [‡] 2002 (Arm I)	Cohort compr surgeries; data		ALIF + PLF + PSS or facet joints screws	DDD	$N_{12}=22$ (only DDD patients) $\stackrel{\circ}{\approx}$	19	22	86 1 year
Christensen [‡] 2002 (Arm II)	Cohort comprised 1-2 level surgeries; data not stratified		PLF + PSS	DDD	$N_{12}=22$ (only DDD patients) *	19	22	86 1 year
Brantigan [‡] 2000	Cohort compr surgeries; data		PLIF + PLF + PSS	DDD	N ₂₄ =91	82	91	90 * 2 years
Hackenberg * 2005	N ₃₆ =39	N ₃₆ =11 (2-level) N ₃₆ =2 (3-level)	TLIF + PLF + PSS	30 DDD + 22 isthmic spondyloli- sthesis	N ₃₆ =52	46	52	89 2 years
Brox [‡] 2003	Cohort compr surgeries; data		PLF + PSS	DDD	N ₁₂ =35	29	35	84 2 years
Delamarter 2009	-	N ₂₄ =61	ALIF + PLF + PSS	DDD	N ₂₄ =61	47	61	77 2 years
Christensen II [‡] 2002	Cohort comprised 1-2 level surgeries; data not stratified		PLF + PSS	DDD	N=20	15	20	77 1 year
Naryan 1997	N34= ₁₂	-	PLF + PSS	DDD	N ₁₂ =34	31	34	91 1 year

Table 2: Literature Control - Radiographic Fusion Outcome

* Results refer to several diagnoses. In addition, subgroup stratification for single- and double level (or more) is not provided for fusion outcome parameter.

^{*} Subgroup stratification for single- and double level (or more) is not provided for fusion outcome parameter.

The number of DDD patients available for radiographic evaluation is assumed to be 22. The authors report the number of operated patients (73) and their stratification to the following 3 sub-groups: 24 with primary degeneration; 25 with secondary degeneration; and 24 with isthmic spondylolisthesis. Of these 73 patients, radiographic evaluation was performed for 67 patients (no stratifications to the 3 sub-groups). As the number of patients in each of the 3 sub-groups is similar, we arbitrary decided that 2 patients in each group were not available for the radiographic evaluation.

• The number of DDD patients available for radiographic evaluation is assumed to be 22. The authors report the number of operated patients (72) and their stratification to the following 3 sub-groups: 19 with primary degeneration; 27 with secondary degeneration; and 27 with isthmic spondylolisthesis. Of these 72 patients, radiographic evaluation was performed for 57 patients (no stratifications to the 3 sub-groups). As the number of patients in each of the 3 sub-groups is similar, we arbitrary decided that 5 patients in each group were not available for the radiographic evaluation.

§ Per CT.

• According to FDA Summary of Safety and effectiveness.

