Fritzell 2002 (Arm I)	N ₂₄ =43 *	N ₂₄ =21 *	ALIF or PLIF + PLF + PSS	DDD	N ₂₄ =65*	47.3 ± 10.9	-	38.5 ± 18.9	8.8	(19%)
Fritzell 2002 (Arm II)	N ₂₄ =35⁴	N ₂₄ =27 •	PSF + PSS	DDD	N ₂₄ =59*	48.4 ± 11.6	-	33.6 ± 17.9	14.8	(30%)
Zigler 2007	N ₂₄ =71	-	ALIF + PLF + PSS	DDD	N ₂₄ =71	62.7 ± 10.3	40.7	39.8 ± 24.3	22.9	(37%)
Hackenberg 2005	No level st	ratification	TLIF + PLF + PSS	DDD	N ₃₆ =30	58.4 ± 18.4	37.5 ± 19.3	37.0 ± 24.8	21.4	(37%)
Delamarter 2009	-	N ₂₄ =61	ALIF + PLF + PSS	DDD	N ₂₄ =61	64.8 ± 9.5	41.1 ± 23.0	38.7 ± 24.1	26.1	(40%)
Brox 2003	No level st	ratification	PLF + PSS	DDD	N ₁₂ =35	42.0 ± 11.0	26.4 ± 16.4	-	15.6	(37%)

Table 4: Literature Control - Oswestrey Disability Index (ODI) Outcome

* The ODI evaluation was conducted for 65 patients, however the stratification to one and two-level was given to 64 patients that were radiographically evaluated.
* The ODI evaluation was conducted for 59 patients, however the stratification to one and two-level was given to 62 patients that were radiographically evaluated.

	Points Range	Number of Manuscripts	Number of Patients	Weighted Average
12m Δ Improvement (single level)	22.0	1	71	22.0
24m Δ Improvement (single level)	22.9	1	71	22.9
12m Δ Improvement (double level)	23.7	1	61	23.7
24m Δ Improvement (double level)	26.1	1	61	26.1
$12m \Delta Improvement (1 \& 2 levels)$	20.9 – 23.7	4	197	23.4
24m Δ Improvement (1 & 2 levels)	8.8 - 26.1	4 (total of 5 study arms)	286	18.5

Table 5: Literature Control - ODI Reference Results

As can be seen, the similar values were reported for one- and 2-level and for one- and two years, justifying the pooling of the results.

Number of Manuscripts	Number of Patients	Weighted Average Improvement (Δ)	Weighted Average Improvement (%)	Ra	nge
5 (a total of 6 study arms)	321	18.22	32.63%	8.8 (19%)	26.1 (40%)

In addition, the recently published systematic literature review (Phillips *et al.*) mentioned above analyzed published literature to evaluate the efficacy of lumbar arthrodesis for DDD patients, reported "*As a whole, these 12 studies including 1420 fusion patients showed a weighted average improvement in ODI function of* $24.7 \pm 6.2/100$ (47.2% change; 95% CI, 41.3–53.1)" [*emphasis added*]. This correlates with the values listed in the tables.

C. VAS Pain

The following table summarizes the VAS (pain) results, as described in the articles referenced above.

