5.8 MISSING DATA

Incomplete information may be available for a subject for various reasons:

- Subject stopped participation in the study at its own request;
- Continuing the follow-up is not possible/subject lost to follow-up;

Subject stopped participation in the study at the Investigator's discretion.

In general, in cases where information will be available for a certain missing data point from a previous and from the next follow-up, an interpolation of the values shall be performed. Missing data from patients that were lost to follow-up will be handle by "last value carried forward" approach (*i.e.*, the last value obtained from a subject will be used for the analysis).

5.9 **PROCEDURES**

5.9.1 **PREOPERATIVE MANAGEMENT**

- a. The Investigator will select the subjects according to the inclusion and exclusion criteria, as described in Sections 5.3 and 5.4, respectively.
- b. The Investigator will be acquainted with the technique and instrumentation required for the procedure. Training will be provided by the Sponsor or its authorized representatives in accordance with the Training Protocol (**Appendix C**).
- c. The Investigator will be familiar with the Protocol of the clinical trial.
- d. Signed written Informed Consent must be obtained for all subjects.
- e. The patients shall be instructed to refrain from the use of NSAIDS for two weeks prior to surgery.
- f. All female subjects who are of child bearing age should present a negative beta-HCG blood (pregnancy) test or submit a signed statement that she is using at least one conventional contraceptive method and that to the best of her knowledge she is not pregnant. Such woman shall be informed of the risks involved in participating in the study while pregnant and cautioned to inform the study personnel if she becomes pregnant during the timeframe of the study.

Pre-procedure assessment will be conducted according to the outline provided in the Case Report Forms (CRFs) booklet.

Pre-procedure examination includes (refer also to Table 8 below):

- Demographic data
- > Full medical history, including concomitant medications

- Physical examination
- Neurological examination
- ➢ X-Ray evaluation

The results of the said examinations shall be recorded.

During the pre-operative session, the following forms shall be completed (refer also to **Table 9** below):

- > Pre-operative CRF

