5.13.3 ANALYSIS POPULATIONS

Intent-to-Treat ("ITT"): All patients treated with the device.

Per-Protocol ("PP"): All patients who did not have a major protocol violation and who completed all study visits.

The primary analysis will be based upon the ITT population. Additional analyses using the PP population will also be presented in the final report.

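### The literature fusion, ODI and VAS figures appear to rest on patients with a follow-up reading, the trial figures compared with them on all treated patients with gaps filled; an observed-reading result should stand beside ITT

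*Combined protocol and SAP*

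**What the plan says.** **Literature side (section 5.2.1).** Most cohort sizes in Table 2 carry a follow-up subscript (24, 12 or 36 months). Numbers operated are given for one study only, a randomised comparison with two arms. For the first arm the footnote reads "Of these 73 patients, radiographic evaluation was performed for 67 patients"; for the second, "Of these 72 patients, radiographic evaluation was performed for 57 patients". The unread patients are then taken out by assumption. In the second arm, "we arbitrary decided that 5 patients in each group were not available for the radiographic evaluation"; in the first, 2 per group. Each arm enters Table 2 with 22 DDD patients.

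Denominators also change with the outcome within a study. One three-technique randomised study has 64 and 62 patients for fusion (Table 2) but 65 and 59 for ODI and VAS (Tables 4 and 6). The footnote to its 65 explains the difference: "however the stratification to one and two-level was given to 64 patients that were radiographically evaluated". The fusion arm of the single-level disc-replacement trial has 69 patients for fusion and 71 for ODI.

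**Trial side.** Section 5.13.3 defines ITT as every patient treated with the device and says "The primary analysis will be based upon the ITT population". The supportive per-protocol set is "All patients who did not have a major protocol violation and who completed all study visits". Under section 5.8, gaps between two visits are interpolated, and for patients lost to follow-up "the last value obtained from a subject will be used for the analysis". Section 5.13.4 adds a case-by-case rule under which some withdrawn patients can be counted as successes.

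**The comparison.** Sections 5.10.1 and 5.10.2 say that the fusion, VAS and ODI results will be compared with section 5.2.1. Section 5.12 defines fusion success as a rate comparable to the literature, without a margin. No section names an analysis set for these comparisons, so by default they fall on ITT.

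**The concern.** A rate among patients with films and a rate among all treated patients answer different questions. If the trial shows 84% against 87.79%, the reader cannot tell whether the gap comes from the device or from how patients without a 24-month film were counted. The same holds for the mean ODI and VAS improvements.

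The per-protocol set does not resolve this. A patient with a valid 24-month film who missed the 6-week visit is excluded from per-protocol but would count in a rate built on available films.

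The direction of the distortion is not fixed. Carrying forward an early non-fused reading lowers the trial rate, while the discretionary success rule in section 5.13.4 raises it. Fusion is first read at 6 months (section 5.10.1), so a patient lost before then has no fusion value to carry.

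**Working it through.** **1. Reproduce the plan's figures.** Summing the 12 arms of Table 2 gives 488 fused of 556, and 488/556 = 87.77% (stated 87.79%). The SD is √(Σnpq)/Σn = 1.37% from the counts and 1.36% from the rounded percentages (stated 1.36%). The half-width for 88% at n = 100 is 1.96 × √(0.88 × 0.12/100) = 6.4 points, as stated.

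**2. Film coverage where numbers operated are given.** 67/73 = 91.8%, so 6 patients (8.2%) are unread. 57/72 = 79.2%, so 15 patients (20.8%) are unread. Both counts cover all diagnoses in the arm.

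**3. Effect on the benchmark.** The footnotes remove 2 + 5 = 7 DDD patients. Restoring them makes the denominator 556 + 7 = 563:
- none of the 7 fused: 488/563 = 86.7%
- all 7 fused: (488 + 7)/563 = 87.9%

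The documented shift is therefore between −1.1 and +0.1 points.

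The second footnote has its own inconsistency. It lists "19 with primary degeneration; 27 with secondary degeneration; and 27 with isthmic spondylolisthesis", which sums to 73 and not 72. The 22 patients used equal 27 − 5, whereas 19 − 5 = 14. Replacing 19/22 by 12/14 gives 481/548 = 87.77%, so the pooled rate does not move.

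Losses in the other arms are not given. As an assumption only, if every arm had lost a share d, the all-operated number would be 556/(1 − d). At d = 8.2% the rate would lie between 80.6% (no missing patient fused) and 88.8% (all fused). At d = 20.8% it would lie between 69.5% and 90.3%.

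**4. Effect on the trial's rate.** Inputs: 88% fused (the plan's assumption in section 5.12, applied here to patients with a reading); m = share without a 24-month reading, assumed 10% to 20% because the plan states no drop-out rate; r = share of filled-in values that are fused. All-treated rate = 0.88(1 − m) + r·m.

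| m | all filled as fused (r = 1) | half (r = 0.5) | none (r = 0) |
|---|---|---|---|
| 10% | 89.2% | 84.2% | 79.2% |
| 20% | 90.4% | 80.4% | 70.4% |

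The shift from the observed rate is m(r − 0.88). A fall of more than 6.4 points needs r below 0.88 − 0.064/0.10 = 0.24 at 10% missing, or below 0.88 − 0.064/0.20 = 0.56 at 20% missing.

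**5. Time points in the literature.** Arms with a 24-month subscript hold 64 + 62 + 69 + 24 + 91 + 61 = 371 of 556 patients. Four arms labelled 1 year hold 22 + 22 + 20 + 34 = 98. Two arms of 52 and 35 carry 36- and 12-month subscripts although their rates are labelled 2 years. Tables 4 and 6 take improvement to the last follow-up and include a 12-month arm of 35 and a 36-month group of 30.

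**The case against.** The strongest case on the other side has several parts.

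- **The benchmark barely moves.** A reader might infer from 57 of 72 that the 86% arm, and so the benchmark, could really be as low as 68%. The documents do not support that. The 57 of 72 covers all diagnoses, the arm enters with 22 patients, and its study supplies 44 of 556 (7.9%). The documented effect is at most 1.1 points. This part stands.
- **The low end on the trial side needs a rule the plan does not contain.** A reader might infer a loss of 10 to 20 points. That requires every missing patient to be filled in as not fused, whereas sections 5.8 and 5.13.4 prescribe interpolation, carrying forward or discretionary success. For illustration, the 6-month rate reported in section 5.14.2 for the ongoing study outside the US is 25/26, on a looser fusion definition. Carrying that rate forward gives 79.2 + 10 × 25/26 = 88.8% at 10% missing and 70.4 + 20 × 25/26 = 89.6% at 20%. This part also stands: the extreme is a bound and not a forecast.
- **No stated decision changes.** A reader might infer that the trial's primary success is at stake. It is not. The primary composite is judged against 41%, fusion alone is evaluated as a secondary endpoint (section 5.12), and the analysis is described as descriptive (section 5.2).
- **A 24-month observed set is not an exact match.** The literature mixes 1-year, 2-year and last-follow-up readings. This is correct. The match is on the type of denominator only.
- **Per-protocol is already a near match.** Only in part: it also excludes patients for missed earlier visits and for major violations.
- **An observed-only rate drops patients without late films, who may include failures.** This is correct, and it is why such a rate should supplement ITT and not replace it.

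The objections reduce the size of the point. They do not remove the mismatch, because no section aligns the two bases.

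**Conclusion.** The mismatch holds, at modest size. The literature figures appear to count patients with a reading. Numbers operated are shown for only two arms, so for the rest this is read from the subscripts and from denominators that differ by outcome. The trial results set against them are by default on all treated patients with filled-in values, and per-protocol does not match either.

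The documented effect on the benchmark is 86.7% to 87.9%. The trial-side effect depends on two unknowns, the loss by 24 months and the fusion status of the values filled in. Under the assumptions above it runs from about 1 to 2 points upward if all carried values are fused to a fall that exceeds the planned ±6.4 only if many of them are non-fused. The direction cannot be stated in advance. The composite and the 41% criterion are not affected. The point concerns whether a planned comparison can be read like for like, and the change is cheap enough to be worth making.

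**What to change.** In sections 5.13.3 and 5.13.4, pre-specify an observed-reading set for each outcome: every treated patient with an actual 24-month reading of that outcome, regardless of other visits or protocol deviations. Wherever fusion, mean ODI improvement or mean VAS improvement is compared with section 5.2.1, report the result in this set beside the ITT result, with the number of patients lacking a reading. State that the literature mixes 1-year, 2-year and last-follow-up readings, so that the match is on denominator type and not on time point. Keep ITT as the primary analysis, and leave the composite and the 41% criterion on it.

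The cost is one more column in the fusion, ODI and VAS tables, with no new data. The downside is that the observed set omits drop-outs. It should therefore appear only beside ITT and only for the literature comparison.

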Several of the studies evaluated fusion using tools and definitions less rigorous than those suggested for the proposed IDE study (*e.g.*, without flexion-extension radiographs, and thus with no motion assessment). Therefore, the reported fusion rates of those articles may be regarded as worst case for the purpose of comparison. On the other hand, one study (*Anjarwalla*) used thin cut CT to evaluate fusion, which is expected to yield a slightly lower fusion rate. Although the proposed study uses radiographs to assess fusion, both studies use x-rays to assess fusion. Therefore, the slight difference in imaging modalities does not preclude using the results of the study when determining the control fusion rate.

Please note, that the ten studies utilized autogenous bone graft (mainly iliac crest bone graft), which is associated with higher fusion rates than allograft.

Overall, the compilation of these ten articles, reporting fusion results for a total of 556 DDD patients, provides for reliable control group for comparison of fusion rate. It is emphasized that all of the mentioned studies were regarded as appropriate for the review of DDD patients in the FDA Executive Summary, and thus are reported in Table 6 of the said document.

Seven of the ten studies report fusion rates at two years, while two studies (*Christensen* and *Nrayan*) reports rates at one year. One study (*Christensen* II) reports fusion rate at both one and two years. Slightly higher fusion rates are expected at two years as compared to one year. As the fusion rate of the subject device is assessed at one year, it is either analogous or worst-case compared to the literature control. Therefore, despite differences in time points, a valid comparison can be made.

Fusion success rates reported in the ten manuscripts, and calculated weighted average of values, are presented in the tables below. The weighting factor is the number of patients in each study.

	Single Level	Double Level	Procedure	Diagnosis	Cohort Size	Fusi N _{fused} /I		Fusion Rate [%]
Fritzell 2002 (Arm I)	N ₂₄ =43	N ₂₄ =21	ALIF or PLIF + PLF + PSS	DDD	N ₂₄ =64	58	64	91 2 years
Fritzell 2002 (Arm II)	N ₂₄ =35	N ₂₄ =27	PSF + PSS	DDD	N ₂₄ =62	54	62	87 2 years
Zigler 2007	N ₂₄ =69	-	ALIF + PLF + PSS	DDD	N ₂₄ =69	67	69	97 2 years
Anjarwalla 2006	N ₂₄ =14	N ₂₄ =10	ALIF + PLF + PSS	DDD	N ₂₄ =24	21	24	88 [§] 2 years

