As shown in the table, the fusion rates reported in the literature control range from 77% to 97%.

The following sections provide for calculation for the control group fusion rates.

For dichotomy (binary) outcome parameters, the following formulas were used to compute weighed average and standard deviation:

Weighted average = $\frac{n1p1 + n2p2 \dots nXpX}{n1 + n2 \dots nX}$ $variance = \frac{n1p1q1 + n2p2q2 \dots nXpXqX}{(n1+n2 \dots + nX)2}$ $SD = \sqrt[2]{variance}$

Where:

p = success probability (fusion)

q = failure probability (1-P)

Weighted average:

=0.8779

Standard deviation:

= 0.0136

 Table 3: Literature Control - Average Fusion Rate

Number of Manuscripts	Number of Patients	Single Level	Double Level	1 or 2 Level	Weighted Average	SD	Range	
10 (a total of 12 study arms)	488/556	234	195	127	87.79%	1.36%	77%	97%

To conclude, the average fusion rate for the control group is 87.79 $\% \pm 1.36\%$.

A recently published systematic literature review, which analyzed published literature to evaluate the efficacy of lumbar arthrodesis for DDD patients ²⁰, reported "*As a whole, these 12 studies including 1420 fusion patients showed...., the fusion rate was* **89.3%** (95% CI, 84.4–94.2)" [*emphasis added*]. This correlates with the above values.

It should be stressed that part of the studies reported in the literature used less stringent definitions of fusion than those used in various IDE studies for lumbar fusion, including the suggested IDE. For example, fusion rate of 74.6% was reported for the control group (Silhouette Spinal Fixation System) of the Dynesys Spinal System (Zimmer Spine) (P070031), and a fusion rate of 88.1% was reported for the control group (LT-CAGE Lumbar Tapered Fusion Device filled with ICBG) in P000058. Use in less stringent fusion definitions results in the relatively higher fusion rates reported in the literature. Further, per FDA's recommendations, the definition of the angular motion in the proposed IDE is even more rigorous (*i.e.* 3° versus 5°) than the fusion definition of previous IDE studies.

B. ODI

The following tables summarize the **ODI results**, as described in the articles referenced above.

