5.12 STUDY SUCCESS CRITERIA

The results of the study at 12 months and 24 months postoperatively for all participating subjects will be evaluated, with reference to the reported results from the

literature, as summarized in **Section 5.2.1**. In addition, assessment of success rate will be conducted at each time point, as applicable.

In addition to evaluating individual patient success as the primary composite endpoint, each element of the composite will be evaluated individually as secondary endpoints, as described below.

Fusion – Success for the fusion outcome measure will be defined as two year fusion rate comparable to the two and one year fusion rates presented in the literature. The pooled results of the Company literature research (for patients with DDD treated with pedicle screws with PLIF/ALIF/TLIF and/or PLF), as presented in **Section 5.2.1**, demonstrated at 12 and 24 months postoperatively fusion rates in the different studies ranging from 77% to 97%.

As discussed in **Section 5.2.1.A**, the weighted average for the fusion rate of the ten articles is 87.79%. Based on the literature, we believe our fusion rate will be 88%.

The assumed fusion rate of 88% has a 95% confidence interval of $\pm 6.4\%$ for 100 patients. Notably, the lower bound of this confidence interval, 81.6%, is within the range of the fusion rates reported in the selected literature.

Safety – Success with regard to safety outcome measure is defined as no worsening in neurological status (motor, sensory, reflex, straight leg raising, and tenderness assessments) and no new permanent neurological deficits (present for at least 2 successive visits at or beyond 6 months), absence of device-related serious adverse events, and absence subsequent surgical interventions at the index level, through 24 months, comparable to neurological deficit, device-related serious adverse events, and subsequent surgical interventions rates presented in the literature.

Based on the literature review in FDA's Executive Summary, the rate of these events in the literature control is 13.5%.

Therefore, the Company estimates that the adverse event rate for these events will be 13.5%. With a sample size of 100 patients, this adverse event rate has a 95% confidence interval of $\pm 6.7\%$.

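### The 1.36% shown as the SD of the literature control fusion rate is a standard error from within-arm variance only; it is mislabelled and moderately too small

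*Combined protocol and SAP*

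**What the plan says.** Section 5.2.1.A builds the fusion benchmark from ten studies (12 arms), "reporting fusion results for a total of 556 DDD patients". On weights it says: "The weighting factor is the number of patients in each study". It states that its "formulas were used to compute weighed average and standard deviation". The variance has a numerator that begins "n1p1q1 + n2p2q2" and a denominator equal to the squared total number of patients; its square root is called the SD. Table 3 prints 1.36% under that label, and the section concludes that the "average fusion rate for the control group" is 87.79% ± 1.36%.

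The spread of the studies is also shown: "As shown in the table, the fusion rates reported in the literature control range from 77% to 97" per cent. The same section says that some studies used looser fusion definitions without motion assessment, one used thin-cut CT, some reported at one year and others at two, and one enrolled two-level surgery only.

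Section 5.10.1 says that the study's fusion rate will be compared with the literature rates of Section 5.2.1. Section 5.12 repeats that "the weighted average for the fusion rate of the ten articles is 87.79" per cent and defines fusion success as a rate comparable to the literature. It assumes 88% with a 95% CI of ±6.4% for 100 patients, and notes that the lower bound, 81.6%, lies within the literature range.

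**The concern.** A figure called an SD and printed after ± is normally read as spread: of patients, or here of study results around their mean. The printed formula gives neither. It is the sampling error of a pooled proportion, and it captures all the uncertainty only if every arm shares one true fusion rate.

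The plan argues against that assumption. It says that looser definitions raise reported fusion rates and cites a control group in another device study at 74.6%. It also quotes a systematic review with a pooled rate of 89.3% and a 95% CI of 84.4 to 94.2, a half-width of 4.9 points. The plan's 1.36% implies 1.96 × 1.36 = 2.7 points, from fewer patients (556 against 1,420).

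At stake is how the benchmark is read when the study's rate is set against it. Taken at face value, ±1.36% makes the comparator look better known than it is, and it misleads a reader who takes it as the scatter to expect between studies.

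**Working it through.** **Inputs.** Fused/total from Table 2, in table order: 58/64, 54/62, 67/69, 21/24, 19/22, 19/22, 82/91, 46/52, 29/35, 47/61, 15/20, 31/34. For the two arms of 22 the plan says: "The number of DDD patients available for radiographic evaluation is assumed to be 22". Two printed percentages differ slightly from their counts (15/20 is 75.0%, printed 77%; 29/35 is 82.9%, printed 84%). Neither affects the conclusion.

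**1. The plan's own figure.**
- Pooled rate = Σx/Σn = 488/556 = 87.77% (plan: 87.79%).
- Σnpq = 57.82, so √57.82/556 = 0.01368, or 1.37 points (plan: 1.36). The printed rounded percentages give 1.36.

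The figure reproduces.

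**2. What it is.** The naive binomial standard error, √(0.8777 × 0.1223/556), is 1.39 points, almost the same. The patient-level SD is √(0.8777 × 0.1223) = 32.8 points, and the SD of the 12 arm rates is 6.1 points. So 1.36% is a standard error of the pooled rate from within-arm variance.

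**3. Heterogeneity.** Pearson's test compares arm counts with the common rate; Cochran's Q depends on the scale.

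| Data | Pearson p | Q p: raw / arcsine / logit | I² |
|---|---|---|---|
| 12 arms | 0.096 (χ² 17.4, 11 df) | 0.02 / 0.07 / 0.18 | 27–51% |
| 10 studies | 0.048 (χ² 17.0, 9 df) | 0.008 / 0.03 / 0.10 | 39–60% |
| 11 arms, without the two-level-only study (47/61) | 0.35 (χ² 11.1, 10 df) | 0.11 / 0.26 / 0.47 | 0–36% |

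The heterogeneity is moderate, depends on the method, and comes largely from one study.

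**4. Standard error with between-study variance.**
- Overdispersion-scaled: 1.39 × √(17.40/11) = 1.75 points (12 arms); 1.91 (10 studies).
- Cluster-robust: 1.91 (12 arms); 1.92 (10 studies).
- DerSimonian-Laird, raw scale: 1.93 (12 arms); 2.13 (10 studies).

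Against 1.36, the ratios run from 1.75/1.36 = 1.3 to 2.13/1.36 = 1.6.

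**5. Random-effects rate, logit DerSimonian-Laird, 12 arms.**
- Weights w = npq, Σw = 57.82. Q = 15.13 on 11 df. C = Σw − Σw²/Σw = 51.61. τ² = (15.13 − 11)/51.61 = 0.080.
- Pooled logit 1.889, SE 0.159, back-transformed to 86.9%.
- 95% CI: 1.889 ± 1.96 × 0.159, giving 82.9 to 90.0%. The plan's figure implies 87.79 ± 2.67, or 85.1 to 90.5%. Widths are 7.1 and 5.4 points, a ratio of 1.3.
- 95% prediction interval for a new study: 1.889 ± 2.228 × √(0.080 + 0.159²) = 1.889 ± 0.723, giving 76.2 to 93.2%.

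On the raw scale the pooled rate is 88.4% (84.6 to 92.2) for 12 arms and 88.3% (84.1 to 92.5) for 10 studies.

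**The case against.** The best defence is that this is a labelling slip with little effect. The pooled rate moves by less than one point, and no decision rests on ±1.36%. Section 5.12 uses the 87.79% average, the 77 to 97% range and a ±6.4% interval for 100 patients. The sample-size text in Section 5.13.1 and the 41% overall-success threshold do not use it, and Section 5.2 calls the analyses descriptive. The range is printed beside the SD in Table 3, and the sources of difference are discussed openly. All of this stands and limits the consequence. It does not make the error bar correct.

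A reader might infer something stronger: that the bar is far too narrow, because the arm rates have an SD of 6.1 points (about 4.5 times 1.36) and six of 12 arms lie outside 87.79 ± 2 × 1.36. The data do not support that. Simulating the 12 arms under one common rate of 87.77% gives an average arm-to-arm SD of 5.3 points, with 6.06 or more in 26% of runs, and puts about seven of 12 arms outside that band. Small arms scatter this much by chance. Both figures compare single arms with the error of a 556-patient mean, so they say little about missing between-study variance.

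**Conclusion.** The point holds in a limited form. The 1.36% is mislabelled, and as the error of the pooled rate it leaves out between-study variance. The shortfall is a factor of about 1.3 to 1.6, so the benchmark is moderately less certain than shown.

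This rests on the counts in Table 2, including the two assumed denominators of 22, and on treating the studies as a sample of settings with differing true rates. The plan's own account of definitions, imaging, levels and visits supports the second assumption. The tests support it only moderately, and weakly once the two-level-only study is removed.

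It would go too far to say that a success rule is miscalibrated, since no threshold in Section 5.12 depends on ±1.36%. Nor do the documents require a prediction interval as the definition of comparable. Its lower limit, about 76%, is close to the 77% already at the bottom of the range in use, so adopting it as a rule would be a matter of preference.

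**What to change.** In Section 5.2.1.A and Table 3:
- Relabel 1.36% as the standard error of the pooled rate (within-arm variance only).
- Report a random-effects pooled rate with its 95% CI, naming the method and scale. With logit DerSimonian-Laird on the 12 arms this is 86.9% (82.9 to 90.0).
- Show a 95% prediction interval for a new study (about 76 to 93%) beside the 77 to 97% range, as descriptive context for the comparisons in Sections 5.10.1 and 5.12.
- Add the result without the two-level-only study as a sensitivity analysis.

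The cost is a short re-analysis of the 12 rows of Table 2, with no change to data collection, sample size or thresholds. The downside is a visibly less precise benchmark.
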